4.5 Definition of Unacceptable Toxicity

For this study we will have a category defined as unacceptable toxicity (UT). This will be used in the statistical design of the phase II part of the study and incorporated into an early stopping rule (see Figure 7-1). If a patient develops UT at any point in the study, he or she will be withdrawn from the study. If more than 1 UT occurs during the final 6 patients of Phase I of the study, the study will be halted for assessment and possible amendment (Figure 7-1).

UT is defined as any grade 5 toxicity, grade 4 neuropsychiatric toxicity or grade 4 clinically significant non-hematologic toxicity thought to be definitely, probably or possibly related to study drug.

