8.1.2 Sample Size Determination

The design incorporates two conditions not usually treated. First, the final group of patients in the phase I component is considered part of the phase II trial. Second, the phase II part has two end-points, toxicity (UT: unacceptable toxicity) and efficacy. The relation between toxicity and efficacy is explicitly taken into account. We test the composite null hypothesis:

$H_0: p(UT) > 0.25 \text{ or } p(PFS > 8 \text{ weeks}) < 0.5 \text{ or } p(PFS > 16 \text{ weeks}) < 0.35$

versus the alternative:

$H_1: p(UT) < 0.05 \text{ and } p(PFS > 8 \text{ weeks}) > 0.66 \text{ and } p(PFS > 16 \text{ weeks}) > 0.56.$

Eleven new patients will be treated in the first stage of the phase 2 component. If 3/17 patients have UTs OR if at most 8/17 are alive and PF at 8 weeks the trial will be either be

suspended for excess toxicity or for futility. The decision for early termination (or amendment) is based on these cut points. If either 3 of 17 stage I patients are DLTs OR if at most 8 of 17 are PF at 8 weeks then terminate or hold up. The final decision point, PFS at 16 weeks is not relevant; the number of such patients does not influence the early decision. The confusion seems to relate to the alternative hypothesis which is couched in terms of 'AND'. It does, of course, require both early and late components of the outcome to be defined. Finally, although 3/17 is less than 0.25, this is the cut point, clearly between 0.05 and 0.25. The early PFS cut point 8/17 is less than 0.5 but is only a cut point.

At that point we will consider protocol amendment. Otherwise, 17 new patients will be recruited. If at least 14/34 patients are PF at 16 weeks AND less than 4/34 have UTs the null hypothesis will be rejected and the treatment declared efficacious. Otherwise it will be declared either too toxic or not efficacious.

Further operating characteristics and statistical details can be found in Appendix 12.3

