12.3 Statistical Considerations and Operating Characteristics for Phase II

Operating characteristics of the design depend on four conditions: toxicity being low (0.05) or high (0.25) and PFS at 16 weeks being low (0.35) or high (0.56). They are summarized below:

1. Toxicity = 0.05 and PFS = 0.56. In this case the power of the study is at least 80%. The chance of early stopping (in error) for excess toxicity is less than 1%. The chance for stopping (in error) for futility varies from 8% to 12% depending on the relation of toxicity to PFS (see details below).
2. Toxicity = 0.05, PFS = 0.35. The chance of early stopping for futility varies from 49% to 57%. The chance of declaring treatment efficacious (type I error) varies from 10% to 21%.
3. Toxicity = 0.25 and PFS = 0.35. Type I error varies from less than 1% to about 5%. Chance of stopping early for either excess toxicity or futility varies from about 26% to about 59%.
4. Toxicity = 0.25 and PFS = 0.56. Type I error varies from about 5% to about 10%. Chance of early stopping for excess toxicity is about 27%.

The term 'UT' here means severe toxicity for which, if frequent enough, dictates dose reduction or trial termination. This early stopping design is an extension of the method of Litwin, Wong and Hudes (Statistics in Medicine, 2007,26:4400-4415). Below, the chance that a patient has a UT and also is PF at 16 weeks is represented by 'a'. 'b', 'c' and 'd', similarly, represent the indicated joint probabilities.

Let $p = p(\text{PFS} > 16 \text{ weeks})$, $p_1 = p(\text{PFS} > 8 \text{ weeks})$ and $p_2 = p(\text{PFS} > 16 \text{ weeks} | \text{PFS} > 8 \text{ weeks})$. Also, let $\text{ptox} = p(\text{UT in 16 weeks})$. Let $\text{ptox1} = f^* \text{ptox} = p(\text{UT in initial 8 week period})$ and $\text{ptox2} = (1-f)^* \text{ptox} = p(\text{UT in 8 through 16 week period} | \text{no UT in the initial 8 weeks})$. Then, $b = p - a$, $c = \text{ptox} - a$ and $d = 1 - a - b - c$. a_1, b_1, c_1 , and d_1 are similarly determined from p_1 and ptox1 . a_2, b_2, c_2 and d_2 are determined likewise, from p_2 and ptox2 .

The table:

$P(\text{UT})$	$1 - p(\text{UT})$	
a	b	$p(\text{PFS} > 16 \text{ weeks}) = 0.56$ (under the alternative hypothesis)
c	d	$p(\text{PFS} < 16 \text{ weeks}) = 0.44$
ptox	$1 - \text{ptox}$	1 ($\text{ptox} = 0.05$ under the alternative hypothesis)

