Illustrates how the joint event probabilities a, b, c and d at the end of the study relate. Namely, if we assign $a = 0.02$ then b, c and d can be determined by subtraction. Here we would get: $b = 0.54$, $c = 0.03$ and $d = 0.41$. For any value of a in $(0, 0.05)$ the other three terms are completely specified. In this design we are considering toxicity to be cumulative. We model the total chance of UT to occur with fraction f in the first interval (0, 8 weeks) and $1-f$ in the final 8 weeks. We have considered fractions $f = 0, 0.25, 0.5, 0.75$ and 1.0 , i.e. $f=0$ implies no toxicity in the first 8 weeks and $f = 1$ implies all toxicity occurs then. The final design is based on $f = \frac{1}{2}$.

P(UT)	1-p(UT)
a1	b1 p(PFS > 8) = 0.66
c1	d1 p(PFS < 8) = 0.34
ptox1	1 - ptox1 1 (ptox1 = ptox2 = 0.025 under the alternative with $f = \frac{1}{2}$) and
P(UT)	1-p(UT)
a2	b2 p(PFS > 16 PFS > 8) = 0.848
c2	d2 p(PFS < 16 PFS > 8) = 0.15
ptox2	1 - ptox2 1

The two tables above characterize the early stopping interval (0, 8 weeks) and final interval (8 weeks, 16 weeks). Numbers in the tables represent the alternative hypothesis. Patients in the initial cohort are represented by the top table (a1, b1, c1, d1) in the initial interval and those who are toxicity and progression free at 8 weeks, hence continue on study are represented by the second table (a2, b2, c2, d2) for their second 8 weeks. Patients recruited into the second cohort, if the study makes it past the first 8 week period, are evaluated only at 16 weeks and are represented by the very first table (a, b, c, d).

The chance of early stopping for excess toxicity, for futility, the chance of final declaration of excess toxicity, the power or type I error were all computed for each of the 4 conditions. Within each of these combinations, the fraction, f, of toxicity born within the first 8 weeks was varied in 5 steps from 0 to 1. We selected the number $f = \frac{1}{2}$ in the belief that toxicity is cumulative and this is the maximum fraction expected to occur in the first half of the trial. Design behavior for $f < \frac{1}{2}$ is ‘better’ than that for $f > \frac{1}{2}$, so is not reported here in detail.

The table below lists the various operating probabilities as functions of ‘a’ for each of the four conditions.

Key:

null = 0: PFS at 16 weeks = 0.35

null = 1: PFS at 16 weeks = 0.56

ntox = 0: Toxicity = 0.05

ntox = 1: Toxicity = 0.25

a: probability that PFS > 16 weeks and patient had UT

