tox: probability of early stopping for excess toxicity

fut: probability of early stopping for futility

toxend: probability that final decision is 'too toxic'

alpha: type I error, probability of declaring efficacy when

either PFS = 0.35 at 16 weeks or toxicity = 0.25

power: probability of declaring efficacy when PFS at 16 weeks is
0.56 and toxicity is 0.05.

null	ntox	a	tox	fut	toxend	alpha	cksum
0	0	0.00	0.0059	0.4938	0.0115	0.2116	1.0000
0	0	0.01	0.0059	0.5105	0.0111	0.1871	1.0000
0	0	0.02	0.0059	0.5271	0.0107	0.1642	1.0000
0	0	0.03	0.0059	0.5437	0.0103	0.1429	1.0000
0	0	0.04	0.0059	0.5602	0.0099	0.1233	1.0000
0	0	0.05	0.0059	0.5766	0.0095	0.1054	1.0000

null	ntox	a	tox	fut	toxend	alpha	cksum
0	1	0.00	0.2690	0.2920	0.3671	0.0493	1.0000
0	1	0.01	0.2690	0.3050	0.3561	0.0451	1.0000
0	1	0.02	0.2690	0.3181	0.3450	0.0410	1.0000
0	1	0.03	0.2690	0.3312	0.3339	0.0369	1.0000
0	1	0.04	0.2690	0.3444	0.3227	0.0329	1.0000

0	1	0.05	0.2690	0.3576	0.3115	0.0291	1.0000
0	1	0.06	0.2690	0.3708	0.3003	0.0255	1.0000
0	1	0.07	0.2690	0.3840	0.2892	0.0221	1.0000
0	1	0.08	0.2690	0.3972	0.2781	0.0189	1.0000
0	1	0.09	0.2690	0.4103	0.2671	0.0161	1.0000
0	1	0.10	0.2690	0.4233	0.2562	0.0134	1.0000
0	1	0.11	0.2690	0.4361	0.2454	0.0111	1.0000
0	1	0.12	0.2690	0.4489	0.2347	0.0091	1.0000
0	1	0.13	0.2690	0.4615	0.2241	0.0073	1.0000
0	1	0.14	0.2690	0.4739	0.2137	0.0058	1.0000
0	1	0.15	0.2690	0.4860	0.2035	0.0045	1.0000
0	1	0.16	0.2690	0.4980	0.1935	0.0035	1.0000
0	1	0.17	0.2690	0.5097	0.1837	0.0026	1.0000
0	1	0.18	0.2690	0.5212	0.1741	0.0020	1.0000
0	1	0.19	0.2690	0.5324	0.1648	0.0014	1.0000
0	1	0.20	0.2690	0.5433	0.1557	0.0010	1.0000
0	1	0.21	0.2690	0.5540	0.1468	0.0007	1.0000
0	1	0.22	0.2690	0.5643	0.1382	0.0005	1.0000
0	1	0.23	0.2690	0.5742	0.1299	0.0003	1.0000
0	1	0.24	0.2690	0.5839	0.1219	0.0002	1.0000
0	1	0.25	0.2690	0.5932	0.1141	0.0001	1.0000

null	ntox	a	tox	fut	toxend	power	cksum
1	0	0.00	0.0059	0.0817	0.0234	0.8759	1.0000
1	0	0.01	0.0059	0.0888	0.0231	0.8653	1.0000

1	0	0.02	0.0059	0.0963	0.0228	0.8535	1.0000
1	0	0.03	0.0059	0.1042	0.0225	0.8404	1.0000
1	0	0.04	0.0059	0.1125	0.0222	0.8259	1.0000
1	0	0.05	0.0059	0.1213	0.0219	0.8099	1.0000

null	ntox	a	tox	fut	toxend	alpha	cksum
1	1	0.00	0.2690	0.0247	0.6054	0.1010	1.0000
1	1	0.01	0.2690	0.0279	0.6021	0.1011	1.0000
1	1	0.02	0.2690	0.0313	0.5985	0.1012	1.0000
1	1	0.03	0.2690	0.0351	0.5947	0.1012	1.0000
1	1	0.04	0.2690	0.0391	0.5907	0.1011	1.0000
1	1	0.05	0.2690	0.0435	0.5864	0.1009	1.0000

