1	1	0.06	0.2690	0.0483	0.5818	0.1006	1.0000
1	1	0.07	0.2690	0.0533	0.5770	0.1002	1.0000
1	1	0.08	0.2690	0.0587	0.5718	0.0997	1.0000
1	1	0.09	0.2690	0.0645	0.5664	0.0990	1.0000
1	1	0.10	0.2690	0.0706	0.5607	0.0981	1.0000
1	1	0.11	0.2690	0.0771	0.5548	0.0970	1.0000
1	1	0.12	0.2690	0.0840	0.5485	0.0957	1.0000
1	1	0.13	0.2690	0.0912	0.5419	0.0941	1.0000
1	1	0.14	0.2690	0.0988	0.5350	0.0923	1.0000
1	1	0.15	0.2690	0.1068	0.5278	0.0901	1.0000
1	1	0.16	0.2690	0.1152	0.5203	0.0877	1.0000
1	1	0.17	0.2690	0.1239	0.5126	0.0850	1.0000
1	1	0.18	0.2690	0.1330	0.5045	0.0819	1.0000

1	1	0.19	0.2690	0.1425	0.4962	0.0786	1.0000
1	1	0.20	0.2690	0.1522	0.4876	0.0749	1.0000
1	1	0.21	0.2690	0.1624	0.4787	0.0710	1.0000
1	1	0.22	0.2690	0.1728	0.4696	0.0668	1.0000
1	1	0.23	0.2690	0.1836	0.4602	0.0625	1.0000
1	1	0.24	0.2690	0.1947	0.4506	0.0580	1.0000
1	1	0.25	0.2690	0.2060	0.4408	0.0533	1.0000

Our analysis above is based on the assumption that toxicity is judged at 8 weeks and again at 16 weeks. In fact, the phase I portion of the study will not last beyond 4 weeks for each patient, so that the initial 3 patients, carried over from phase I, could become UT at 8 weeks. The tables above assume that the number of UTs at 8 weeks (not 4 weeks) is at most one. To account for this possibility, we re-computed the table assuming no restriction on the first 6 patients, but using only the early stopping rules for toxicity at 8 weeks. Thus the initial phase II cohort of all 17 patients in this re-computation are all treated alike. The results are shown in the next table. While the table above allows a smaller chance of toxicity than the actual trial, the table below allows a greater chance of toxicity in the initial phase II cohort. The main difference in the two computations is that the chance of early stopping for UT is about 9% higher under the re-computation conditions (35%) than it is under the top table (27%).

Operating characteristics of design with no restriction on the first 6 patients other than those tested at 8 or 16 weeks.

null	ntox	a	tox	fut	toxend	alpha	cksum
0	0	0.00	0.0082	0.4937	0.0114	0.2106	1.0000
0	0	0.01	0.0082	0.5103	0.0110	0.1862	1.0000
0	0	0.02	0.0082	0.5269	0.0106	0.1633	1.0000
0	0	0.03	0.0082	0.5434	0.0102	0.1421	1.0000
0	0	0.04	0.0082	0.5599	0.0098	0.1227	1.0000
0	0	0.05	0.0082	0.5762	0.0094	0.1049	1.0000

null	ntox	a	tox	fut	toxend	alpha	cksum
0	1	0.00	0.3591	0.2586	0.3197	0.0429	1.0000
0	1	0.01	0.3591	0.2700	0.3100	0.0393	1.0000

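### Appendix 12.3, item 3 understates early stopping: with toxicity 0.25 and PFS 0.35 the appendix's own table gives 56% to 86% for either reason, not 26% to 59%

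*Combined protocol and SAP*

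**What the plan says.** Appendix 12.3 opens with four numbered items that summarise how the phase II design behaves under low or high toxicity and low or high PFS.

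- Item 3 (toxicity 0.25, PFS 0.35): "Chance of stopping early for either excess toxicity or futility varies from about 26% to about 59"%.
- Item 4 (toxicity 0.25, PFS 0.56): "Chance of early stopping for excess toxicity is about 27"%.

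The tables that follow report early stopping in two separate columns, one for toxicity and one defined as "fut: probability of early stopping for futility". After the first table the appendix gives the condition behind it: "The tables above assume that the number of UTs at 8 weeks (not 4 weeks) is at most one". It then prints a second table without that restriction on the first six patients.

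The rules being evaluated are in section 8.1.2. Six patients carry over from phase I, and "Eleven new patients will be treated in the first stage of the phase 2 component". The trial is suspended "If 3/17 patients have UTs OR if at most 8/17 are alive and PF at 8 weeks". Section 4.5 adds a separate rule: "If more than 1 UT occurs during the final 6 patients of Phase I of the study, the study will be halted".

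**The concern.** Item 3 gives a probability for stopping for either of two reasons. In the table for that scenario, the toxicity column alone is 26.9% in every row and the futility column alone is never below 29.2%. If the two columns are separate outcomes, a combined 26% cannot occur, and 59% is only the largest futility entry.

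Section 4 says the design is meant to stop early for futility and toxicity. The four items are the plan's short account of how well it does so. Someone who reads only the summary would conclude that a toxic and inactive regimen might be stopped at the first stage only about a quarter of the time. The tables say more than half.

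**Working it through.** **Inputs**

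- First stage: 6 + 11 = 17 patients. Stop for toxicity at 3 or more UTs; stop for futility at 8 or fewer progression free at 8 weeks (section 8.1.2).
- UT rate over 16 weeks 0.25. Half falls in the first 8 weeks (Appendix 12.3: "The final design is based on" f = 1/2), so the 8-week UT rate is 0.125.
- 8-week PFS under the null: 0.50 (section 8.1.2).
- a = probability of being progression free at 16 weeks and having a UT, from 0 to 0.25. I took the 8-week value as a/2. The appendix does not spell out this scaling, but it reproduces the printed entries.

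**Step 1. Reproduce the toxicity column.** Let X be the UTs among the first 6 and Y those among the 11 new patients, both binomial with rate 0.125.

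- P(X = 0) = 0.4488 and P(X = 1) = 0.3847, so P(X ≤ 1) = 0.8335.
- P(Y ≥ 3) = 0.1497 and P(Y ≥ 2) = 0.4081.
- First table: (0.4488 × 0.1497 + 0.3847 × 0.4081) / 0.8335 = 0.2242 / 0.8335 = 0.2690, as printed.
- Second table: P(3 or more of 17) = 0.3591, as printed.

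**Step 2. Reproduce the futility column.** Each patient falls into one of four cells (UT or not, progression free or not). Futility means at most 2 UTs in 17 and at most 8 patients progression free without a UT. The exact multinomial sums are:

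| Table | a = 0 | a = 0.25 |
|---|---|---|
| First (at most 1 UT in first six) | 0.2920 | 0.5932 |
| Second (no restriction) | 0.2586 | 0.5216 |

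All four match the printed values. The match requires that trials stopped for toxicity be excluded from the futility count, so the two columns do not overlap.

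**Step 3. Confirm from the printed rows that the columns add.**

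- PFS 0.56, toxicity 0.25, a = 0: 0.2690 + 0.0247 + 0.6054 + 0.1010 = 1.0001. The four outcomes use up all the probability, apart from rounding.
- PFS 0.35, toxicity 0.25, a = 0: 0.2690 + 0.2920 + 0.3671 + 0.0493 = 0.9774. The remaining 0.0226 is a final decision of not efficacious, which has no column of its own.
- With 8-week PFS of 0.50, the probability of 8 or fewer of 17 is exactly 0.50. The second table's 0.2586 at a = 0 is possible only if toxicity stops have been taken out first.

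**Step 4. Add the columns for item 3's scenario.**

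| Table | Lowest | Highest |
|---|---|---|
| First | 0.2690 + 0.2920 = 0.561 | 0.2690 + 0.5932 = 0.862 |
| Second | 0.3591 + 0.2586 = 0.618 | 0.3591 + 0.5216 = 0.881 |

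Against the first table, item 3 is low by 56.1 − 26 = 30.1 points at the bottom and 86.2 − 59 = 27.2 points at the top.

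**Step 5. Check the other items.** Item 1's early-stopping figures (below 1%; 8% to 12%) agree with 0.0059 and with 0.0817 to 0.1213. Item 2's 49% to 57% agrees with 0.4938 to 0.5766, the upper end truncated. Item 4's 27% agrees with 0.2690. Only item 3's range fails.

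**The case against.** **Each reason taken separately.** Item 3 could be read as spanning the two reasons one at a time, from a truncated 0.2690 to 0.5932. The sentence does not say that, and items 1, 2 and 4 name a single reason when they mean one. The source of the 26% cannot be settled: 0.2690 truncated and the second table's futility minimum of 0.2586 both fit. The correction is the same either way.

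**Little harm done.** The correct entries are printed in the same appendix, the trial acts on the 3/17 and 8/17 rules rather than on this sentence, and the error understates protection. All of this stands, and it keeps the point to a text correction.

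**The 27% is already explained.** This also stands. Item 4 matches its table, and the text after that table states the condition and gives the unrestricted result, which it prints as 35% (0.3591 rounds to 36%). What is missing is a label in the summary.

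**A stronger reading to avoid.** A reader might infer that the 27% is itself wrong because halts under the six-patient rule in section 4.5 are left out, and that the true figure is 37% to 39%. That arithmetic is 0.1665 + 0.8335 × 0.2690 = 0.391 if the rule is judged at 8 weeks, or 0.367 if it is judged at 4 weeks with half of the 8-week UTs assumed to have occurred by then. The documents do not support it:

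- It treats the six carried-over patients as unselected. Table 4-3 makes every UT a DLT, and Table 4-2 with section 4.2 takes a dose forward only after 0 of 3 or at most 1 of 6 DLTs in 28 days.
- After 0 of 3, the six-patient rule can fail at 4 weeks only if 2 or more of the 3 added patients have a UT. With half of the 8-week UTs by week 4 (rate 0.0625), that is 3 × 0.0625² × 0.9375 + 0.0625³ = 1.1%, and the total early toxicity stop is 31.0%. Given at most 1 UT in six at 4 weeks, the total is 33.4%.
- If 25% to 100% of the 8-week UTs fall before week 4, the totals run from 33.5% down to 26.0% after 0 of 3, and from 35.2% down to 26.9% given at most 1 of 6. None reaches 37%. These figures use UTs only and ignore other DLTs.
- The 39% also needs the rule judged at 8 weeks, whereas the appendix says phase I lasts no more than 4 weeks per patient.
- Section 4.5 frames the rule as applying to phase I, so conditioning the phase II characteristics on passing it is a defensible choice.

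**Conclusion.** Item 3 is wrong as written. On the appendix's own model, a regimen with toxicity 0.25 and PFS 0.35 stops early for one reason or the other with probability 56% to 86% (first table) or 62% to 88% (second table). The result rests only on printed entries and on the two columns being mutually exclusive, which the row totals and an exact reproduction both confirm. It keeps the appendix's assumption that half of the toxicity falls in the first 8 weeks.

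Item 4 is not an arithmetic error. Its 27% is the right conditional figure, quoted without its condition. Decision cut points, sample size, type I error and power are untouched, and the error makes the design appear slower to stop than it is.

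**What to change.** In item 3, replace the range with 56% to 86% and name the first table as its source. If the unrestricted table is to be primary, use 62% to 88% and name that table instead.

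In item 4, label the 27% as conditional on at most one UT in the first six patients, and give the unrestricted table's 36% beside it. No figure combining the section 4.5 halts with these should be added on the present documents.

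The cost is two sentences in the appendix. No rule, sample size or analysis changes.

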4.4 Duration of Study

From a study perspective, the anticipated duration of study being open for enrollment will be 2 years. Amongst Fox Chase Cancer Center and its community partners (FCCC) there were 450 analytic (new to the system without ever having had any treatment for their RCC) cases of RCC in 2012 alone and FCCC saw approximately 224 of those cases. Out of these cases at FCCC ~35/year were de novo metastatic and ~30/year were locally advanced and thus at high risk for short-term metastatic progression. In addition, ~30 non-analytic (primary treatment conducted elsewhere) cases per year were seen at FCCC sites.

According to the FCCC RCC database 256 nephrectomies were performed in 2010, 234 in 2011, 227 in 2012 and 204 in 2013. Over 75 new patients with RCC were seen by GU medical oncology in 2013 and over 43 patients with RCC were enrolled on therapeutic clinical trials. Given this volume of patients we believe we can accrue 1-2 patients a month to this trial.

Once an eligible patient is identified and consented, screening will occur within 28 days of study initiation (first day of drug administration). The patient will stay on study unless he or she has PD or unacceptable toxicity or chooses to withdraw consent. Once a patient is no longer on active treatment, follow up for progression and survival will occur for a maximum of 2 years.

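### Appendix 12.3 uses two incompatible unacceptable-toxicity models and a UT count that differs from section 8.1.2, so its stated type I errors and power are not those of the written rule

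*Combined protocol and SAP*

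**What the plan says.** Section 8.1.2 sets the phase II rule. Stage 1 has 17 patients: six carried over from phase I and 11 new. The trial is held up if there are 3 UTs among them, or if 8 or fewer are progression-free at week 8. Otherwise 17 more are recruited, and the null hypothesis is rejected on this condition: "If at least 14/34 patients are PF at 16 weeks AND less than 4/34 have UTs".

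Appendix 12.3 gives the operating characteristics. It defines ptox as the probability of a UT within 16 weeks. A fraction f, set to 1/2, splits it into ptox1 for weeks 0-8 and ptox2 = (1 - f) x ptox for weeks 8-16. The appendix labels ptox2 as conditional on having had no UT in the first interval.

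In stage 1, "those who are toxicity and progression free at 8 weeks, hence continue on study are represented by the second table". For stage 2, "Patients recruited into the second cohort, if the study makes it past the first 8 week period, are evaluated only at 16 weeks", and these patients follow one 16-week table.

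For condition 4 the appendix states: "Toxicity = 0.25 and PFS = 0.56. Type I error varies from about 5% to about 10" per cent. Condition 3 (toxicity 0.25, PFS 0.35) is given as below 1% to about 5%, and power under condition 1 as 80% or more.

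Progression ends participation in both cohorts. Section 4.4 says: "The patient will stay on study unless he or she has PD or unacceptable toxicity or chooses to withdraw consent". Sections 4.2 and 6.13 also end treatment at progression.

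**The concern.** The two cohorts receive the same regimen under the same stopping rules, so they should have the same 16-week UT probability. In the appendix they do not. Stage 1 patients who progress by week 8 have no further UT risk. Stage 2 patients keep the full 16-week risk whatever happened at week 8.

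After stage 1, the limit of fewer than 4 UTs in 34 is the only numeric toxicity criterion. Condition 4 is the plan's statement of how often a regimen with too much toxicity but good PFS would still be declared efficacious. If that figure comes from a mixed model, or from a count other than the one in section 8.1.2, the plan does not say how much protection the rule gives.

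**Working it through.** **Inputs (section 8.1.2 and Appendix 12.3).** For condition 4: "b1 p(PFS > 8) = 0.66" and "null = 1: PFS at 16 weeks = 0.56", so p2 = 0.56/0.66 = 0.848. With ptox = 0.25 and f = 1/2, ptox1 = ptox2 = 0.125. The overlap a, the probability of both a UT and 16-week PFS, runs from 0 to 0.25, with a1 = a2 = a/2. The first six patients are conditioned on at most one UT by week 8, as the first set of tables assumes. Success means progression-free without a UT.

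**Step 1: reproduce the plan.** Exact enumeration of the joint UT and progression-free counts gives, at a = 0, early stopping for toxicity 0.2690, for futility 0.0247, a final too-toxic decision 0.6054 and a declaration of efficacy 0.1010, all as printed. All 26 rows of the condition 4 block match to four decimals (range 0.0533-0.1012). Spot-checked rows of the other blocks match too (0.8759, 0.2116, 0.0493).

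The match needs one thing that the text does not say: stage 1 UTs from weeks 0-8 must be dropped from the final count. Up to two such UTs can be present when the trial continues. Applying the rule as section 8.1.2 words it gives 0.0356 at a = 0, not 0.1010.

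**Step 2: the 16-week UT rate in each cohort.** In stage 1 it is ptox1 + b1 x ptox2, with b1 = 0.66 - a/2.

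- a = 0: 0.125 + 0.66 x 0.125 = 0.2075
- a = 0.25: 0.125 + 0.535 x 0.125 = 0.192

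In stage 2 it is 0.25 by construction. With PFS 0.35 (week-8 PFS 0.50), stage 1 gives 0.172-0.1875.

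**Step 3: the conditional label.** If ptox2 is conditional on no earlier UT, then even with no progression the two intervals give 0.125 + 0.875 x 0.125 = 0.234, not 0.25. A conditional value that restores 0.25 is (0.25 - 0.125)/(1 - 0.125) = 0.143.

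**Step 4: consequences for condition 4 (ranges over a).**

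| UT model | Week 0-8 stage 1 UTs left out (table basis) | All UTs among 34 counted (8.1.2) |
|---|---|---|
| As printed | 5.3-10.1% | 2.2-3.6% |
| Stage 2 given the stage 1 process, ptox2 = 0.125 | 12.4-17.1% | 5.7-7.0% |
| Same process in both, ptox2 = 0.143 | 10.3-13.5% | 4.6-5.3% |
| 0.25 kept as the 16-week probability in both cohorts | about 2.8-5.9% | about 1.0-1.9% |

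For the last row, stage 1's second-interval risk is raised to 0.125/b1 (0.125/0.66 = 0.189 at a = 0), so that it also totals 0.25. The overlap a2 is kept within its feasible limits, so these values are approximate.

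**Step 5: condition 3 and power.**

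| UT model | Counting | Condition 3 | Power |
|---|---|---|---|
| As printed | table basis | 0.01-4.9% | 81.0-87.6% |
| As printed | all 34 | 0.01-2.1% | 78.4-84.5% |
| Stage 1 process in both, ptox2 = ptox/2 | table basis | 0.3-8.7% | 82.4-88.4% |
| Stage 1 process in both, ptox2 = ptox/2 | all 34 | 0.2-4.3% | 80.3-86.0% |

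With the printed UT models and the written count, power falls below 80% at the high end of a (78.4% at a = 0.05).

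**The case against.** A reader might infer that the true chance of passing a regimen with a 25% UT rate is 12-17% rather than 5-10%. The documents do not support that, for three reasons.

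- **The count.** The 12.4-17.1% comes from a count that omits stage 1 UTs from weeks 0-8. Section 8.1.2 requires them. With them counted, the same UT process gives 5.7-7.0%, inside the stated range. For condition 3 the corresponding 0.2-4.3% also lies within what is stated.
- **The meaning of 0.25.** The appendix defines ptox over 16 weeks, and the hypothesis in section 8.1.2 does not restrict it to time on treatment. On that definition stage 1 is the understated part, and the error falls. The 12-17% needs 0.25 to be the risk of a patient who stays on treatment. After that change the regimen's 16-week UT probability is only about 19-21%.
- **Ptox2.** The figure keeps ptox2 at 0.125. With a proper conditional value it is 10.3-13.5%.

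Other points also carry weight. Section 7.2 collects serious events through 30 days after the last ixazomib dose, and related ones later. Some UTs after a week-8 progression would therefore be seen, and zero later risk is a simplification. Section 8.1.6 allows the monitoring committee to review toxicity as often as every 3 months. Section 8.1.1 describes the analyses as estimation only.

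These points limit the size and direction of the problem. They do not remove it. Two UT rates for one regimen cannot both hold, and 5.7-7.0% falls within 5-10% because two departures offset each other. The estimation-only remark sits beside a rule in section 8.1.2 that formally rejects a null hypothesis, with stated error rates.

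**Conclusion.** The stated operating characteristics are wrong as written. They mix two UT models, treat an unconditional share of ptox as a conditional probability, and use a final count that is not the one in section 8.1.2. The figures for conditions 1, 3 and 4 were therefore not calculated for the written rule under any single model.

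The direction is not fixed. For condition 4 the figure runs from about 1-2% (0.25 as a 16-week probability in both cohorts, all UTs counted) to 12.4-17.1% (stage 1 process in both cohorts, week 0-8 UTs omitted). Only the all-UTs column corresponds to the written rule, and there the range is about 1% to 7%. On that count the clearest loss is in power: 78.4-84.5% with the printed UT models.

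These results assume f = 1/2, at most one UT among the first six, no UTs recorded after week-8 progression (except in the printed stage 2 model and the fixed-0.25 reading), and PFS rates as in the appendix. Without the restriction on the first six, the printed 4.65-8.88% becomes 10.8-15.0% on the table basis, and 4.9-5.9% with all UTs counted, when stage 2 is given the stage 1 process.

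**What to change.** 1. State whether 0.05 and 0.25 are 16-week UT probabilities, as the appendix defines ptox, or risks while on treatment.
2. Use one UT process for both cohorts, with ptox2 a true conditional probability: (ptox - ptox1)/(1 - ptox1). If 0.25 is to be the 16-week probability with progressors leaving at week 8, the divisor must instead be the proportion who continue (b1), as in the last row of step 4.
3. Count all UTs among the 34 patients, as section 8.1.2 says.
4. Re-run the program, reissue both sets of tables, and restate conditions 1-4.

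The cost is a program re-run and edits to Appendix 12.3. The recalculation itself changes nothing for patients or visits. Some stated figures may become less favourable, and if power then falls below 80% the sponsor would have to accept that or revisit the design.

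### Appendix 12.3 gives the early toxicity stop only at f = 1/2; under the plan's own belief about f, the 27–36% shown for a 25% UT regimen is an upper bound, and the modelled chance is 6–9% at f = 0.25 and 0% at f = 0

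*Combined protocol and SAP*

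**What the plan says.** Section 8.1.2 sets the stage 1 rule: "If 3/17 patients have UTs OR if at most 8/17 are alive and PF at 8 weeks", the trial is suspended for toxicity or for futility. The 17 are six patients carried over from phase I and eleven new ones.

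Appendix 12.3 takes a UT probability over 16 weeks that is either low ("ntox = 0: Toxicity = 0.05") or high ("ntox = 1: Toxicity = 0.25"). It splits that probability in time: "We model the total chance of UT to occur with fraction f in the first interval (0, 8 weeks"), and the remainder in weeks 8–16. It reports that "We have considered fractions $f = 0, 0.25, 0.5, 0.75$ and 1.0" were examined, and selects f = 1/2 "in the belief that toxicity is cumulative and this is the maximum fraction expected to occur in the first half of the trial". Behaviour for f below 1/2 is called better than for f above 1/2, "so is not reported here in detail".

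Both sets of printed tables are for f = 1/2. For the high-toxicity, good-PFS condition the summary says: "Chance of early stopping for excess toxicity is about 27" per cent. The second set of tables, with no restriction on the first six patients, prints 0.3591 for the same event.

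**The concern.** If 1/2 is the largest share of UT expected in the first 8 weeks, the plausible range is f from 0 to 1/2. The modelled stage 1 toxicity stop sees only UTs in each patient's first 8 weeks, so its chance of firing on a toxic regimen rises with f. The single value reported is then the most favourable one in the expected range, and the unfavourable values are set aside with a remark that does not fit this characteristic.

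Section 4 says the design is meant to stop early for toxicity as well as futility. The 3/17 look is the only numeric toxicity rule between the six-patient halt in Section 4.5 and the final 4/34 test. Someone reading the summary in 12.3 would credit it with about a one-in-three chance of catching a 25% UT regimen before 17 more patients are treated. The plan's own view that toxicity accumulates implies less.

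**Working it through.** **Inputs.** True UT over 16 weeks: 0.25 or 0.05. Risk per patient in weeks 0–8: p = f × UT. Stop if at least 3 UTs in 17 = 6 + 11 patients. First set of tables: at most 1 UT in the first six. Second set: no such restriction. All from Appendix 12.3 and Section 8.1.2.

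**Reproducing the printed figures (f = 1/2, UT = 0.25, p = 0.125).**

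- No restriction: 1 − P(X ≤ 2 | 17, 0.125) = 1 − (0.1033 + 0.2509 + 0.2867) = 0.3591, as printed (the text rounds it to 35%).
- At most 1 UT in the first six: [P(0 of 6) × P(≥ 3 of 11) + P(1 of 6) × P(≥ 2 of 11)] / P(≤ 1 of 6) = (0.4488 × 0.1497 + 0.3847 × 0.4081) / 0.8335 = 0.2690, as printed.
- At UT = 0.05 the same formulas give the printed 0.0082 and 0.0059.

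**The same formulas at f = 0.25 (p = 0.0625).**

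- No restriction: 1 − (0.3338 + 0.3783 + 0.2018) = 0.0861.
- Restricted: (0.6789 × 0.0276 + 0.2716 × 0.1478) / 0.9505 = 0.0619.

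**All five values of f, early toxicity stop at UT = 0.25.**

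| f | at most 1 UT in first six | no restriction |
|---|---|---|
| 0 | 0% | 0% |
| 0.25 | 6.2% | 8.6% |
| 0.5 (printed) | 26.9% | 35.9% |
| 0.75 | 51.4% | 64.3% |
| 1 | 71.7% | 83.6% |

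On the comparison the appendix makes, f below 1/2 against f above 1/2, the stop is weaker: 0–9% against 51–84%. Counting the Section 4.5 halt (more than 1 UT in the last six phase I patients, applied at the 8-week rate) as a stop as well gives 39.1%, 10.8% and 0% at f = 0.5, 0.25 and 0, the same pattern.

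**Other characteristics.** An exact calculation of the whole design matched the first set of tables to four decimals at the smallest and largest a (the joint probability of UT and being progression-free at 16 weeks) in all four conditions. Moving f from 0.5 to 0.25 to 0 in that calculation:

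- False toxicity stop at UT 5%: 0.8% to 0.1% to 0% without restriction; 0.6% to 0.1% to 0% with it.
- Wrongly declaring efficacy at UT 0.25, PFS 0.56, a = 0.25: 5.3% to 4.6% to 3.0%.
- Power at a = 0.05: 81.0% to 82.0% to 82.3%. The gain is not uniform: at a = 0, power goes from 87.6% to 86.8% to 85.5%.

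**If the look counts every UT seen to date.** Section 8.1.2 can be read this way. Assumptions of the simulation: random entry at 1–2 patients a month (the rate in Section 4.4), UT times uniform within each 8-week interval, the look 8 weeks after patient 17 enters, f from 0 to 0.5.

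| Exposure of week-8 progressors | stop at UT 25% | false stop at UT 5% |
|---|---|---|
| remain fully at risk | about 72–80% | about 3–4% |
| no later UT, 8-week PFS 0.66 | about 42–69% | about 1–3% |
| no later UT, 8-week PFS 0.50 | about 26–62% | about 0.5–2% |

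**The case against.** The strongest reply is that nothing printed is miscalculated. The 0.2690 and 0.3591 are exact for f = 1/2, the text discloses that only this value is tabulated, and its remark concerns design behaviour as a whole. That stands. A reader might infer that the remark is wrong throughout; the working does not support this, since the false-stop rate improves at smaller f, and so do power and the false-efficacy rate in the configurations quoted. It needs qualifying, not deleting.

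A second reply is that the weak figures belong to the model and not clearly to the trial. In Section 8.1.2 the 8-week qualifier attaches to progression-free status, and the UT clause has no window. A reader might infer that the operating rule itself has only a 0–9% chance of stopping a toxic regimen; the documents do not establish that. But 12.3 judges toxicity at 8 weeks, and the secondary UT endpoint in Section 3 is also at 8 weeks, so the ambiguity is real and the printed characteristics apply to only one reading.

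Third, f = 0 is the edge of a sensitivity grid and is never called expected. Fair: it is a bound, and f = 0.25 is the more useful figure.

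Fourth, other safeguards exist: withdrawal of any patient with UT and the six-patient halt (4.5), a monitoring committee that may review toxicity every 3 months and can recommend ending accrual (8.1.6), and the final rule. These limit the harm, but the committee review has no numeric threshold and the final rule acts only after stage 2.

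**Conclusion.** The concern holds as one of incomplete and partly misdescribed reporting. Under the plan's own belief that at most half of UT arises in weeks 0–8, 27–36% is the upper end of the modelled chance of stopping early on a 25% UT regimen. Like for like, 26.9% falls to 6.2%, and 35.9% to 8.6%, at f = 0.25; both are 0% at f = 0. These results use the appendix's own model and need no outside figure.

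What weakens is early protection, not the final decision. At UT 0.25, PFS 0.56 and a = 0.25 the chance of wrongly declaring efficacy stays at about 3–5% for f of 1/2 or less, but that verdict comes after the second 17 patients are treated, unless futility or another safeguard stops the trial first.

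It is also tempting to conclude that counting all UTs to date would restore a stop probability of 72–80%. That requires patients who progress by week 8 to stay fully at risk of UT. Section 6.13 ends treatment at progression, and 12.3 carries into the second interval only patients free of both toxicity and progression. If week-8 progressors have no later UT, the range is about 42–69% or 26–62%, depending on 8-week PFS.

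**What to change.** 1. In 12.3, qualify the remark about smaller f so that it excludes the early toxicity stop. Print the f = 0 and f = 0.25 results, which the appendix says were computed. State that 27–36% is the upper end of the expected range, with 6–9% at f = 0.25 and 0% at f = 0.
2. Reconcile 8.1.2 with 12.3. State which UTs count at the stage 1 look, those in each patient's first 8 weeks or all those observed by the date of the look, and give operating characteristics for that rule with the assumption about progressors stated.

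The first change costs a sentence and one table. The second costs a sentence and, if all UTs to date count, a recomputation: the false stop at 5% UT would be about 0.5–4% depending on the progressor assumption, against 0.6–0.8% printed at f = 1/2. The effect on power should be computed before any figure is stated. Neither change adds patients.
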